8.2.4.4. Laboratory Evaluations of Special Interest

The number and percentage of maximum on-treatment grade 0 through 4 for serum creatinine, ALT, AST, platelets, neutrophils, WBC, and hemoglobin and grade 1 through 5 for eGFR will be summarized. Descriptive statistics for time to first event, duration of any grade event, and cumulative duration of grade 3b/4/5 for eGFR and grade 3/4 events for others will be calculated. Shifts from baseline to maximum on-treatment grade will also be presented.

A listing will be provided for patients who potentially meet the Hy's law criteria. Potential is defined as meeting these 3 criteria any time during the study (non-concurrent): AST or ALT level of $\geq 3 \times$ upper limit of normal (ULN), total bilirubin level of $> 2 \times$ ULN, and alkaline phosphatase level $< 2 \times$ ULN. Total Bilirubin, AST, ALT, and alkaline phosphatase will be listed.

8.2.4.5. Non-study Medications

The percentage of patients using non-study medications prior to, during, and after the treatment period will be summarized.

A listing of non-study medications data will be reported.

8.2.4.6. Cross Intolerance

The percentage of patients experiencing cross intolerance to imatinib, dasatinib, or nilotinib will be summarized overall and by AE. The recurrence percentage of those grade 3/4 TEAEs during treatment with bosutinib will also be estimated.

8.2.4.7. Death

The number of deaths within 28 days of last dose and cause of these deaths will be summarized.

8.2.4.8. Adverse Events

The number and percentage of AEs listed below will be summarized overall and by MedDRA SOC and PT. Sorting will be done alphabetically by SOC and then by decreasing frequency of PT. AEs may also be summarized by other levels if deemed appropriate (eg, Higher Level Group Term [HLGT]).

- TEAEs;
- AEs leading to treatment discontinuations;
- TEAEs leading to dose reductions;
- TEAEs leading to dose delays;
- TEAEs by maximum toxicity grade (grades 1 to 5);
- TEAEs of higher toxicity grades (grades 3 or 4);
- TEAEs related to test article;
- Serious adverse events (SAEs);
- COVID-19 related TEAEs;
- TEAEs before and after initial dose reduction to 400 mg, 300 mg, and 200 mg due to an AE.

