3. STUDY DESIGN

This is a single-arm, open-label, non-randomized, multi-center Phase 4 study to evaluate bosutinib (Bosulif®) in patients with chronic or advanced CP/AP/BP Ph+ CML who have failed prior treatment with TKIs which are commercially available, due to drug resistance or intolerance, or are otherwise contraindicated for treatment with commercially available TKIs such as imatinib, dasatinib, and nilotinib (i.e., presence of a BCR-ABL mutation or medical condition making commercially available TKIs unsuitable for a patient). Patients will receive bosutinib for at least 4 years from the time of first dose, unless disease progression, unacceptable toxicity, withdrawal of consent by patient, death or discontinuation of study by Sponsor. Patients discontinuing bosutinib prior to completing 4 years of therapy will be followed for survival until they complete at least 4 years on study of follow-up from the time of first dose. Patients completing at least 4 years of bosutinib with continued benefit may be switched to commercially available therapy at that time.

Cytogenetic and Molecular assessments will be performed at baseline and every 3 months until Week 52, then at 6 -month intervals during Years 2, 3, and 4 of treatment. Complete blood counts should be performed weekly for the first month, then 4 weeks later and thereafter per the visit schedule ([Table 1](#)) and as clinically indicated.

Hematologic, cytogenetic and extramedullary disease assessments will be done locally, while molecular monitoring of BCR-ABL transcript levels and mutational analysis of the BCR-ABL kinase domain will be performed by a central laboratory and carried out by independent central analysis. Local cytogenetic assessment will be repeated at least 28 days later to confirm on-treatment CCyRCML disease status (when the CCyR is first observed in the absence of MMR). Patient participation will conclude no sooner than 4 years after first dose.

Approximate Duration of Study: The end of the study will be considered to be the last visit of the last patient for purposes of closing out sites, informing the site or regional institutional review board/ethics committee (IRB/EC), and terminating distribution of Council for International Organizations of Medical Sciences (CIOMS) reports; however, for other purposes the end of the study will be the last patient last visit.

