2.1. Study Design

This is a single-arm, open-label, non-randomized, multi-center Phase 4 study to evaluate bosutinib (Bosulif®) in patients with CP/AP/BP Ph+ CML whose disease has failed prior treatment with commercially available TKIs due to drug resistance or intolerance, or are otherwise contraindicated for treatment with commercially available TKIs such as imatinib, dasatinib, or nilotinib (ie, presence of a BCR-ABL mutation or medical condition making commercially available TKIs unsuitable for a patient). Patients will receive bosutinib for at least 4 years from the time of first dose, unless disease progression, unacceptable toxicity, patient withdrawal of consent, death or Sponsor discontinuation of study. Patients discontinuing bosutinib prior to completing at least 4 years of therapy will be followed for survival until they complete at least 4 years of follow-up from the time of first dose. Patients completing at least 4 years of bosutinib with continued benefit may be switched to commercially available therapy at that time.

Patients are allocated to the cohort based on the derived assignment from the baseline disease stage and prior TKI therapy. Patients are either:

- CP Ph+ CML second line (CP2L) resistant or intolerant to imatinib, dasatinib, or nilotinib;
- CP Ph+ CML third line (CP3L) resistant or intolerant to imatinib and dasatinib, imatinib and nilotinib, or dasatinib and nilotinib;

- CP Ph+ CML fourth or later line (CP4L) resistant or intolerant to imatinib, dasatinib, and nilotinib;
- AP Ph+ CML second line (AP2L) resistant or intolerant to imatinib, dasatinib, or nilotinib;
- AP Ph+ CML third line (AP3L) resistant or intolerant to imatinib and dasatinib, imatinib and nilotinib, or dasatinib and nilotinib;
- AP Ph+ CML fourth or later line (AP4L) resistant or intolerant to imatinib, dasatinib, and nilotinib;
- BP Ph+ CML second line (BP2L) resistant or intolerant to imatinib, dasatinib, or nilotinib;
- BP Ph+ CML third line (BP3L) resistant or intolerant to imatinib and dasatinib, imatinib and nilotinib, or dasatinib and nilotinib;
- BP Ph+ CML fourth or later line (BP4L) resistant or intolerant to imatinib, dasatinib, and nilotinib, or
- Ph- CML.

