6.2. Safety Endpoints

Treatment-emergent adverse events (TEAE) are defined as any event increasing in severity from baseline or any new event starting during bosutinib therapy or within 28 days of the last dose of study drug (using 28 day lag).

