6.2.1. Exposure and Compliance

Exposure and compliance data will be collected during this study. The primary exposure endpoints while the patient is on treatment are duration of treatment, cumulative dose received, dose over time, reasons for dose modifications (reduction, delay, or escalation), and reasons for treatment discontinuation. Duration of treatment is the time from first non-zero dose to last non-zero dose ([date of last non-zero dose – first dose date +1]/30.4). Planned dose is 500 mg/day.

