8.2.2. Analysis of Secondary Efficacy Endpoints

The response rate and DOR analyses are based on the evaluable analysis set for Ph+ CML patients only. The efficacy analysis is the percentage of responders cumulative anytime on-treatment or at a specific landmark, for:

- Cumulative MCyR separately for CP, AP, and BP;
- Cumulative confirmed OHR separately for AP2L, AP3L, AP4L, BP2L, BP3L, BP4L;
- Best response separately for CP, AP, and BP;
- Landmark MCyR at 3, 6, 12, 18, and 24 months separately for CP, AP, and BP;
- Landmark confirmed OHR at 3, 6, 9, 12, 18, and 24 months separately for AP and BP;
- Cumulative confirmed CHR separately for CP, AP, and BP;
- Cumulative MMR separately for CP, AP, and BP;
- Duration of CCyR separately for CP, AP, and BP;
- Duration of MMR separately for CP, AP, and BP.

Any patient not demonstrating a response on-treatment for cumulative and at the specific visit for landmark is deemed a non-responder for the respective analysis. For landmark analyses, if the patient is missing the landmark assessment however the patient is responding at the scheduled before and after visit (eg, missing Month 6/Week 26 but responding at Week 13 and Week 39, missing Month 18/Week 78 but responding at Week 52 and

Week 104, etc.), then the patient will be deemed a responder for that landmark. For cumulative MMR (including MR⁴ and MR^{4.5}) and MCyR (including CCyR), supportive analyses will be provided excluding patients with baseline response and also for patients who responded before and after initial dose reduction to 400 mg, 300 mg, and 200 mg due to an AE

The duration of cytogenetic and molecular response analyses are based on the evaluable analysis set for the subset of patients who respond for the respective endpoint. The K-M method, as described in [Section 8.1](#), will be used for estimation of the distributions of duration provided most responding patients remain on treatment until progression or loss of response. The percentages of CCyR and MMR for the respective endpoint, along with percent of censored patients still on-treatment and percent of reasons for failure will be summarized.

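### The before/after dose-reduction summaries have no defined periods, denominators or exposure adjustment, so their percentages can differ in either direction with no change in event rate

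*SAP*

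**What the plan says.** SAP 8.2.4.8 sets one measure for all its adverse event tables: "The number and percentage of AEs listed below will be summarized overall and by MedDRA SOC and PT". One of the listed tables is "TEAEs before and after initial dose reduction to 400 mg, 300 mg, and 200 mg due to an AE".

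SAP 8.2.2 adds supportive analyses of cumulative MMR (with MR4 and MR4.5) and cumulative MCyR (with CCyR), "also for patients who responded before and after initial dose reduction to 400 mg, 300 mg, and 200 mg due to an AE". The general measure in that section is a percentage: "The efficacy analysis is the percentage of responders cumulative anytime on-treatment or at a specific landmark". No denominator is given for the split itself.

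The rest of the plan does not fix the length of either period:

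- **TEAE window (SAP 6.2).** It includes "any new event starting during bosutinib therapy or within 28 days of the last dose of study drug", so it spans the whole of treatment and 28 days more.
- **Planned treatment (SAP 2.1).** "Patients will receive bosutinib for at least 4 years from the time of first dose", subject to early stopping.
- **Exposure (SAP 6.2.1).** "Duration of treatment is the time from first non-zero dose to last non-zero dose". This is a total per patient. It is not divided at a dose reduction and is not used as a denominator for adverse events.
- **AEs of special interest (SAP 6.2.8 and 8.2.4.9).** Time to first event and event duration are summarised, but not by period before or after reduction.
- **Population (SAP 8.2.4).** The full analysis set is the default. Nothing says whether the before and after columns are limited to patients who had a reduction.
- **Further dose changes (Protocol 5.2.2, footnotes to Tables 3 and 4).** Re-escalation is allowed. The SAP does not say whether the period after reduction to one level ends at a further reduction or at a re-escalation.

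**The concern.** The percentage of patients with at least one event rises with the time observed. If one period is short and the other long, the longer one shows the higher percentage even when the event rate is identical in both. Here each patient's periods are set by when the reduction happened and when treatment stopped, and nothing makes them equal.

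The response split can suffer in the same way, because responses are found only at assessments and the number of assessments on each side of the reduction varies. Patients already in response on the reduction date cannot have a first response afterwards, and the SAP does not say where they are counted.

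A before/after table by dose level invites a reading about tolerability or retained efficacy at lower doses. The study is meant to support conversion of a conditional authorisation, so that reading could carry weight even though no test is attached to it.

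**Working it through.** **Stated figure.** The plan gives no figure for these tables, so there is nothing to reproduce.

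**Inputs.** The percentage measure, the split and the absence of person-time come from SAP 8.2.4.8 and 8.2.2. The documents give no event rate, time to reduction or time after it. These are assumptions: 0.02, 0.05 and 0.10 events per patient-month, with reduction at month 3 of 24, month 6 of 12 or month 9 of 12.

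**Step 1. Same rate before and after.** P(at least one event) = 1 − exp(−rate × months).

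At 0.05 per patient-month:

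- Month 3 of 24: 1 − exp(−0.05 × 3) = 13.9% before; 1 − exp(−0.05 × 21) = 65.0% after.
- Month 6 of 12: 1 − exp(−0.05 × 6) = 25.9% in both.
- Month 9 of 12: 1 − exp(−0.05 × 9) = 36.2% before; 1 − exp(−0.05 × 3) = 13.9% after.

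| Rate per patient-month | Month 3 of 24 | Month 6 of 12 | Month 9 of 12 |
|---|---|---|---|
| 0.02 | 5.8% v 34.3% | 11.3% v 11.3% | 16.5% v 5.8% |
| 0.05 | 13.9% v 65.0% | 25.9% v 25.9% | 36.2% v 13.9% |
| 0.10 | 25.9% v 87.8% | 45.1% v 45.1% | 59.3% v 25.9% |

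The rate is the same on both sides of every cell. At 0.05 per patient-month it is 0.05 × 12 = 0.60 per patient-year before and after.

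**Step 2. Reduction triggered by an AE.** A simulation of 400,000 patients used 10 event types with equal constant rates, follow-up of 12, 24 or 48 months, and a fixed chance that any event triggers the reduction. Only patients with a reduction were kept. Nothing changes at the reduction.

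| Rate per type per month; trigger chance | One event type, before v after | Any event, before v after | Events of one type per patient-month, before v after |
|---|---|---|---|
| 0.05; 0.3 | 25.1% v 59.9% | 100% v 97% | 0.052 v 0.050 |
| 0.05; 0.1 | 40.9% v 55.9% | 100% v 95% | 0.054 v 0.050 |
| 0.02; 0.3 | 21.3% v 31.7% | 100% v 87% | 0.024 v 0.020 |

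The any-event row moves the opposite way from the single-event rows, because the triggering event puts every reduced patient in the before column. Person-time rates remove most of the gap. What remains comes from keeping only patients whose triggering event fell within follow-up.

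**Step 3. Response assessments.** Protocol 3 states: "Cytogenetic and Molecular assessments will be performed at baseline and every 3 months until Week 52". After that they are six-monthly. From Table 1 the on-treatment visits are Weeks 13, 26, 39, 52, 78, 104, 130, 156 and 182, with End of Treatment at Week 208, so 10 in all for a patient who completes four years.

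- Reduction before Week 13: 0 scheduled assessments before, 10 after.
- Reduction at Week 20: 1 before, 9 after.
- Reduction at Week 30: 2 before, 8 after. If treatment ends at Week 52, it is 2 before and 2 after.

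With an assumed constant 15% chance of response per visit through Week 104, reduction at Week 20 gives 15% before (one visit) and 1 − 0.85^5 = 56% after (five visits) among those not yet in response.

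**The case against.** The strongest reply is that these summaries are descriptive. SAP 4.1 and 4.2 rule out hypotheses, decision rules and tests, the response split is called supportive, and the AE table is one bullet of ten. That stands: the point concerns how a secondary display can be read.

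Second, the size and direction rest on assumed periods. That also stands. SAP 8.2.2 reports that more than 80% of patients were off treatment by 11 March 2020, but neither document says how long patients spent on each side of a reduction. A reader might infer that the after column will be the larger because treatment is planned for years. The documents do not support this: the gap vanishes with equal periods and reverses with a late reduction.

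Third, exposure time is not the only influence. A reader might infer that it alone sets the direction. It does not: the split is at an AE-driven reduction, and Protocol 1.2.2 reports from the earlier first-line phase 3 study that diarrhea was concentrated in the first one to two months and then improved. Such an event falls with time whatever the dose. This makes the planned table harder to interpret, and it also means that rates per patient-year are not a full cure.

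Fourth, the layout of the response split is inferred. The wording in SAP 8.2.2 could mean only that responders are classified by when they responded relative to the reduction. A reader might infer that paired raw percentages are planned, but the section does not say so. What can be said is that no denominator or at-risk set is given.

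**Conclusion.** The point holds as a gap in definition and measure. Following SAP 8.2.4.8 as written gives two percentages over patient-specific periods that will usually differ in length, with no exposure adjustment anywhere in the SAP. At a constant 0.05 events per patient-month the before and after figures run from 13.9% v 65.0%, through no difference, to 36.2% v 13.9%, depending only on when the reduction falls. These values rest on assumed rates and times, so they show the mechanism and do not predict the trial's results.

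Two further features affect the reading. Among reduced patients the any-TEAE percentage before reduction is close to 100% by construction, and early-onset events decline regardless of dose. A reader might infer that exposure-adjusted rates would turn the table into an estimate of what dose reduction does. They would not: with no true change, the simulation still gave 0.024 before and 0.020 after per patient-month in one setting, and front-loaded events would add to this.

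Nothing here touches the primary endpoints or any test. It is a cheap improvement to a descriptive display, worth making before the tables are produced.

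**What to change.** In SAP 8.2.4.8 and 8.2.2, for each dose level:

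1. State which patients are included.
2. State the start and end of the before and after periods, including whether the after period ends at a further reduction or at a re-escalation.
3. State whether a patient who had the event before the reduction is at risk again after it.
4. Beside the percentages, give patients with an event per patient-year at risk, with a 95% CI and the total exposure in each period.
5. For response, report two groups separately. For patients already in response on the reduction date, report whether they keep it. For patients not in response on that date, report the cumulative incidence of first response from that date. SAP 8.1.4 already specifies a cumulative incidence method with treatment discontinuation as the competing risk.
6. Add a footnote that the reduction is triggered by an AE and that AE rates change over time, so neither the percentages nor the rates estimate an effect of dose reduction.

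Dose dates and event dates are already collected. The cost is a little more programming and a longer table.

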8.2.4.9. Adverse Events of Special Interest

The number and percentage of maximum treatment-emergent CTCAE grade events and successful rechallenge for ALT, AST, thrombocytopenia (including MedDRA PT Platelet Count Decreased), neutropenia (including PT Neutrophil Count Decreased), leukopenia (including PT White Blood Cell Count Decreased), anemia (including PT Hemoglobin Decreased), diarrhea, nausea, vomiting, cardiac toxicity, vascular toxicity, and renal toxicity will be summarized. Descriptive statistics for time to first event, duration of any grade event, and cumulative duration of grade 3/4 events will be calculated for selected parameters.

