Cytogenetic Assessment ^k	X			X	X	X	
Molecular Assessment ^k	X			X	X	X	
Mutation Analysis ^l	X					X	
Extramedullary Disease Assessment ^m	X		As clinically indicated ⁿ			X	
Adverse Events			Continuous			X	
Concomitant Medications			Continuous			X	
FACT-Leu	X		X	X	X	X	
Blood and plasma for biobanking ^o	X		As clinically indicated ⁿ			X	
Hepatitis B serology ^q	X		As clinically indicated				
Survival							X ^o

The 3-monthly visits will be performed at approximately 13-week intervals.

- a. The use of TKIs could lead to cumulative long-term cardiovascular disease therefore smoking status will be collected. Past and present smoking status will include: smoking type (if the patient ever smoked), if the patient is a current smoker, or ex-smoker and, if appropriate, duration since the patient last stopped smoking, and the number of units consumed/day (e.g. number of cigarettes; number of pipes; number of cigars, etc.).
- b. Contraceptive Check: patients of child-bearing potential will be required to affirm their use of 2 highly effective methods of contraception until 28 days after their last dose of bosutinib which will be documented in the patient's source document.
- c. Hematology to include complete blood count (CBC) including a WBC with differential, platelet count, and neutrophil count (see [Appendix 9](#)). Complete blood counts should be performed weekly for the first month, then 4 weeks later and thereafter per the visit schedule, and as clinically indicated.
- d. Direct bilirubin must be collected if total bilirubin is $> 1.5 \times \text{ULN}$ and for any Hy's Law determination, if appropriate (see Section [Appendix 9](#)).
- e. Coagulation tests including: either prothrombin time (PT) or international normalized ratio (INR); and partial thromboplastin time (PTT) or activated partial thromboplastin time (aPTT).
- f. A urine or serum pregnancy test should also be done whenever one menstrual cycle is missed during treatment (or potential pregnancy is otherwise suspected). Pregnancy tests may also be repeated as per request of IRB/ECs or if required by local regulations.
- g. Standard of care chest X-ray results may be used for screening if not longer than 12 weeks prior to the first bosutinib dose in the absence of past medical history of pulmonary disease. If the patient has past medical history of pulmonary disease or ongoing pulmonary co-morbidities chest X-ray should be obtained within 7 days prior to the first bosutinib dose.

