6.2.3. Laboratory Evaluations of Special Interest

Laboratory parameters including but not limited to alanine aminotransferase (ALT), aspartate aminotransferase (AST), serum creatinine, estimated glomerular filtration rate (eGFR), platelets, neutrophils, WBC, and hemoglobin will be summarized. Endpoints include distribution of maximum toxicity, time to first event (time from first dose to date of first event including only non-partial dates), duration of any grade event (time from start date to stop date including only non-partial dates), and cumulative duration of grade 3b/4/5 events for eGFR and grade 3/4 events for others (sum of time from start dates to stop dates including only non-partial dates for all events).

eGFR will be derived based on the Modification of Diet in Renal Disease (MDRD) study formula: $175 \times \text{SerumCreatinine}^{-1.154} \times \text{age}^{-0.203} \times 1.212$ (if patient is black) $\times 0.742$ (if female), creatinine measured in mg/dL. eGFR will be graded according to the Kidney Disease Improving Global Outcomes (KDIGO) Kidney function stages (Grade 1: ≥ 90 , Grade 2: $60 < 90$, Grade 3a: $45 < 60$, Grade 3b: $30 < 45$, Grade 4: $15 < 30$, and Grade 5: $< 15 \text{ mL/min/1.73 m}^2$).

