6.2.8. Adverse Events of Special Interest

Adverse events including ALT, AST, thrombocytopenia (including MedDRA preferred term [PT] Platelet Count Decreased), neutropenia (including PT Neutrophil Count Decreased), leukopenia (including PT White Blood Cell Count Decreased), anemia (including PT Hemoglobin Decreased), diarrhea, nausea, vomiting, cardiac toxicity (definition to be determined before DBL), vascular toxicity (definition to be determined before DBL), and renal toxicity (definition to be determined before DBL) will be summarized. Additional AEs or AE clusters may be summarized if deemed appropriate. AE characteristics to be

summarized include maximum toxicity, time to first event, duration of any grade event, cumulative duration of grade 3/4 events, and successful rechallenge (those patients who were re-dosed and did not discontinue bosutinib due to this AE after having a dose delay).

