8. STATISTICAL METHODOLOGY AND STATISTICAL ANALYSES

8.1. Statistical Methods

8.1.1. Analyses of Continuous Data

For continuous variables, the descriptive statistics include n, mean, median, standard deviation (SD), and range (minimum, maximum).

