8.1.4. Analyses of Time-To-Event Endpoints

For time-to-event endpoints such as time to response, DOR, time to transformation, PFS, and OS, the method of analysis will either be Kaplan-Meier (K-M) or cumulative incidence of the event adjusting for the competing risk of treatment discontinuation due to any reason without the event (Gray).¹

When applying the K-M method, medians and quartiles with the associated 2-sided 95% CI will be provided. The CIs based on the Brookmeyer-Crowley log(-log) transformation method will be provided. The K-M yearly rates up through year 4 with the associated 2-sided 95% CI based on Greenwood's formula using a log(-log) transformation will also be provided.

When applying the cumulative incidence method, yearly rates up through year 4 with the associated 2-sided 95% CI based on the delta method using a log(-log) transformation will be provided.

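### Cardiac, vascular and renal toxicity are summarised by crude percentages and uncensored event times with no exposure-adjusted rate, so the tables cannot separate risk from time on drug or show a rising rate

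*SAP*

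**What the plan says.** - **Frequency.** SAP 8.2.4.9 plans "The number and percentage of maximum treatment-emergent CTCAE grade events and successful rechallenge" for a list of adverse events of special interest that ends with cardiac, vascular and renal toxicity.
- **Timing.** The same section adds "Descriptive statistics for time to first event, duration of any grade event" and the cumulative duration of grade 3/4 events, but only for a selection of parameters. It does not name the parameters. SAP 6.2.8 covers the whole set, including these three toxicities, and says the characteristics to be "summarized include maximum toxicity, time to first event, duration of any grade event" and others.
- **Method.** For continuous variables SAP 8.1.1 says "the descriptive statistics include n, mean, median, standard deviation (SD), and range (minimum, maximum"). The only written definition of the quantity is for laboratory parameters, in SAP 6.2.3: "time from first dose to date of first event including only non-partial dates". No censoring rule goes with it. SAP section 7 names only efficacy and survival endpoints when it assigns censoring.
- **Method available but not assigned here.** SAP 8.1.4 offers Kaplan-Meier or "cumulative incidence of the event adjusting for the competing risk of treatment discontinuation due to any reason without the event". Its examples are time to response, duration of response, transformation, PFS and OS.
- **Window and layout.** SAP 6.2 counts events on drug or within 28 days of the last dose. SAP 8.2.4 reports safety by phase and line cohort. Treatment duration is summarised separately (SAP 8.2.4.2), and no event rate per unit of exposure is planned.
- **Why time matters here.** Protocol Table 1, footnote a: "The use of TKIs could lead to cumulative long-term cardiovascular disease therefore smoking status will be collected". Protocol 4.3 separately describes a decline in eGFR over time on bosutinib. The protocol's safety endpoint includes the timing of adverse events.

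**The concern.** A patient without the event has no event date. With no censoring rule, that patient drops out of the mean and median. What remains is timing among patients who had the event while still under observation, and early discontinuation removes the late events. The crude percentage depends on exposure in the same way, because a patient who stops at 6 months has little chance to show a harm that appears in year 3.

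Two things are at stake. First, cohorts will sit side by side in the safety tables. If their time on drug differs, they will look different in cardiovascular or renal risk even when the hazard is the same. Second, a harm that builds up with time on drug shows as a rate that rises from year to year, and neither planned summary can display that.

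**Working it through.** The documents contain no figure for these events to reproduce, so this is an illustration under stated assumptions.

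**Inputs**
- Maximum time on drug of 4 years (SAP 2.1).
- Median time on drug *m* of 11 months, the median duration of therapy of the larger earlier Phase 1/2 study in Protocol 1.2.2, used as an assumption. The contrast of 36 months is also an assumption.
- Exponential discontinuation, μ = ln 2 / *m*.
- Event hazard λ = 0.03 per year, an assumption.
- The 28-day tail is ignored in steps 1, 2 and 4.

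**Step 1. Planned summaries, constant hazard.** Let s = λ + μ.
- Crude proportion: P = (λ/s)(1 − e^(−4s)).
- Median time among events: the *t* that solves 1 − e^(−st) = ½(1 − e^(−4s)).

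| | *m* = 11 months | *m* = 36 months |
|---|---|---|
| μ per year | 0.756 | 0.231 |
| s per year | 0.786 | 0.261 |
| 1 − e^(−4s) | 0.957 | 0.648 |
| Crude percentage | 3.65% | 7.45% |
| Median time among events | 9.9 months | 18.0 months |

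The hazard is identical in both columns. The 4-year risk under continued treatment is 1 − e^(−0.12) = 11.3%.

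**Step 2. Rate per patient-year.** Expected time at risk per patient is (1 − e^(−4s))/s.
- *m* = 11: 1.217 years, so 3.65/1.217 = 3.0 per 100 patient-years.
- *m* = 36: 2.482 years, so 7.45/2.482 = 3.0 per 100 patient-years.

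**Step 3. What drives the median event time.** This run includes the 28-day tail and a constant hazard.
- With *m* = 11 months, moving the 4-year on-drug risk from 5% to 30% moves the median only from 10.1 to 9.4 months.
- With that risk held at 10%, moving from no discontinuation to *m* = 11 months moves the median from 23.3 to 10.0 months.
- A milder discontinuation scenario, 37% off drug by 24 months (taken from the earlier Phase 3 study in Protocol 1.2.2), gives 18.1 months and a crude 6.7% at that same 10% risk.

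**Step 4. Rising hazard** (Weibull shape 2, 15% risk by year 4; assumed). The cumulative hazard is ct², with c = −ln(0.85)/16 = 0.01016.
- Crude percentage: 2.7% (*m* = 11) and 8.4% (*m* = 36). Median among events: about 21 and 30 months, against 33 with no discontinuation.
- Rate in year *k*, approximately 100c(2k − 1): 1.0, 3.0, 5.1 and 7.1 per 100 patient-years. With discontinuation included, the values are 0.9, 2.9, 4.9, 7.0 (*m* = 11) and 1.0, 3.0, 5.0, 7.1 (*m* = 36).
- The overall rate is 2.2 (*m* = 11) and 3.3 (*m* = 36), so a total rate alone does not remove the exposure effect when the hazard rises. The split by year on drug is needed.

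**Step 5. Does the 8.1.4 cumulative incidence change the percentage?** Simulation of 400,000 patients, constant hazard, 10% on-drug risk:

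| Discontinuation | Follow-up | Crude | Cumulative incidence | 1 − Kaplan-Meier |
|---|---|---|---|---|
| 37% off by 24 months | complete | 6.8% | 6.8% | 10.1% |
| *m* = 11 months | complete | 3.4% | 3.4% | 10.1% |
| 37% off by 24 months | 12 to 36 months (assumed) | 4.2% | 5.6% | 7.6% |
| *m* = 11 months | 12 to 36 months (assumed) | 2.7% | 3.2% | 7.4% |

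The last two rows are evaluated at 36 months. With complete follow-up, cumulative incidence equals the crude figure. It differs only when follow-up is incomplete.

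**The case against.** **The percentage answers a legitimate question.** The SAP counts events on drug or within 28 days. The share of treated patients with such an event is a valid on-treatment risk, and at the final analysis it is complete. This stands. A reader might infer that the plan reports these harms as too rare, but the documents do not support that as a general statement. The percentage is low only against the risk under continued treatment, or at the first analysis (SAP section 3), when each patient has at least one year of follow-up but entry was staggered.

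**Cumulative incidence does not correct for discontinuation.** A reader might infer that applying the 8.1.4 method would remove the distortion. Step 5 shows that it would not. Once follow-up is complete it gives the same percentage and reaches half its 4-year value at the same time as the median among events. Its value is to put timing on all treated patients and to handle incomplete follow-up at the first cut.

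**The text is less definite than it looks.** SAP 8.2.4.9 does not name the parameters that get timing statistics, and the list in 8.1.4 is given as examples. That only patients with events contribute is inferred from the missing censoring rule. This stands as a caution. Because SAP 6.2.8 lists time to first event for these toxicities, the reading is the natural one. If it is wrong, their timing is not reported at all.

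**The sizes are not this trial's.** This also stands. The 11 months is a duration of therapy at a data cut, not a median time to discontinuation, and may overstate attrition. The SAP's statement that more than 80% were off treatment by March 2020 may include patients who completed 4 years.

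**The study is descriptive and treatment duration is shown.** This is true, but a separate duration table does not let a reader rebuild a rate for each toxicity or see it by year on drug.

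**Conclusion.** The point holds in a limited form. For cardiac, vascular and renal toxicity the plan offers a crude on-treatment percentage, an uncensored summary of event times for parameters it leaves unnamed, and no exposure-adjusted rate. Both summaries depend strongly on time on drug. Under the assumptions above, one hazard produces percentages that differ twofold (3.65% and 7.45%) and median event times of 9.9 and 18.0 months. A rate rising from about 1 to 7 per 100 patient-years over four years would not be visible as such. The direction follows from the method; the size rests on assumed hazards and discontinuation. The cumulative-harm rationale in the protocol footnote is cardiovascular only. The renal part rests on Protocol 4.3.

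**What to change.** In SAP 8.2.4.9, for cardiac, vascular and renal toxicity:

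1. Add first events per 100 patient-years at risk, where time at risk is time on drug plus 28 days, up to the first event. Give exact Poisson 95% intervals, in total and by year on drug, per cohort and overall.
2. Show timing by the 8.1.4 yearly cumulative incidence on all treated patients. State that it handles incomplete follow-up at the first analysis and does not correct for discontinuation.
3. Label any mean or median time to first event as being among patients with the event, and name the parameters that receive it.
4. Keep the crude percentages.

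A baseline smoking summary would be a useful option but is not needed for this fix.

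**Cost.** SAP wording and a few tables from data already collected. Intervals will be wide in small cohorts. For example, 45 patients with 1.217 years at risk each give 54.8 patient-years. Two events there give 3.7 per 100 patient-years, with an exact 95% interval of about 0.4 to 13.2 (0.242/54.8 and 7.225/54.8). The split by year will be wider still, so it will be most readable overall and in the larger cohorts.
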